#### Time-integrated NOx and NO2 samples

The analysis of time-integrated NOx and NO2 samples, collected with Ogawa passive samplers, require temperature (T) and relative humidity (RH) values to obtain estimates of the concentrations over the sample period. We will compute mean T and RH for each Ogawa deployment period based on measurements of the co-located eLichens monitors. If T and RH data are unavailable for any Ogawa samples, we will impute the average conditions from other homes sampled as close in time to these data as possible.

#### Identification and analysis of self-reported cooking data

The survey responses about cooking will be pulled from the electronic data collection system for the 1 or more weeks prior to the intervention and 1 or more weeks after the intervention. (Pull from REDCap download directly to R)

- How often was the gas stove or oven used in your home over the last week: Breakfast, lunch, dinner, other times (never, 1-2 days, 3-4 days, 5+ days)
- If food was being cooked, how often was it: Fried, deep fried, grilled, steamed/boiled, toasted, electric pot cooker, baked, microwaved
- Think about the burner you used the most this week. Is it one of the burners in the front or back? (front/back/my stove doesn't have front and back burners)
- In the last week, how often was the stove hood fan used during cooking? (never, rarely, occasionally, frequently)

#### Identification and analysis of events associated with monitored cooking burner and range hood use

Since the intervention was designed to increase range hood use and reduce in-home concentrations of pollutants resulting from cooking (leading to overall pollutant exposure reduction), the analysis of environment and range hood use outcomes will start with the identification of cooking burner usage events. These events will be identified by analysis of the temperatures measured by thermocouples adjacent to cooktop burners, T/RH sensors above the oven vent, and T/RH sensors mounted above the cooktop, on/in the range hood. Events of range hood usage will be identified by analysis of data collected by the anemometer mounted in the path of airflow for the range hood. And the magnitudes of air pollutant concentration increases resulting from cooking will be quantified by analysis of the time series data from the eLichens monitor. The pollutant event magnitudes will also be referenced to the amount of cooking burner use.

When burners were used, and in some cases, also from cooking that occurred in the homes, it is expected that concentrations of air pollutants increased at the monitoring location, which was typically 1-2 rooms away from the kitchen. The concentration profile should be related to the emissions characteristics (total mass emitted, emission duration, quality or pattern of emissions), the volume of all the spaces into which the emissions mixed (starting from the kitchen), and the rate of removal processes such as mixing into farther rooms, outdoor air ventilation, filtration, deposition etc. Since many emission events occur over time periods that are shorter than removal rates, a common pattern in the kitchen and often also closely connected spaces, is for a sharp or gradual increase of pollutant concentrations, reaching a distinct peak value, followed by a decay that reflects a combination of additional mixing and removal processes. For a consistent set of transport and removal processes, the peak height will be proportional to the magnitude of total emissions. When emissions occur

over periods longer than removal processes, the pollutant concentration may achieve a roughly steady value, or “steady state”. Again, with removal processes constant, the magnitude of steady state would be proportional to emissions, and inversely proportional to the aggregate rate of removal processes. Conversely, differences in peak height for a short term emission event and differences in steady state levels for longer emission events, could result from different emissions, different removal rates, or both.

Another common feature of indoor air pollutant concentration patterns in the room with the source, and sometimes an adjacent room, is a faster initial decay from the peak that reflects mixing from the room to other rooms, or within a very large room (e.g., a “great room” of an open floor plan home), followed by a slower first order decay that reflects removal from the space, e.g. by outdoor air ventilation, deposition, etc.

Kitchen ventilation can reduce exposures related to cooking by (1) removing the pollutants at the source, before they mix into the home, and by (2) increasing the removal rate through higher overall ventilation.

#### Identify cooking events

The analysis will start with identification and characterization of cooking *burner activity* and *cooking events*.

- Individual instances of potential *burner activity* will be identified algorithmically and checked / adjusted based on visual review. For each incidence of an individual burner temperature signal increasing in a manner that suggests potential use the analysis will identify the start time of the temperature increase, the time when temperatures start to decrease back to baseline (i.e. accounting for potential resetting of the burner to a lower temperature for steady cooking), peak temperature above the baseline prior to the increase, and mean rate of temperature increase (fitted).
- If the thermocouple was placed closely adjacent to the burner, the start of a burner at any setting of medium or above should provide a signal of temperature increasing much more rapidly than would occur from even the most extreme environmental drivers (e.g. direct sunlight hitting the site through a window, or room air heated by heating system). The temperature increase will continue as the pot on the burner is heated, and gradually reduces its own rate of heat absorption from the flame and increases its own contribution to the adjacent thermocouple by radiation and increasing convective heat transfer. A pot being held at constant temperature is expected to provide a relatively stable temperature at the adjacent thermocouple. Adjusting the burner to a smaller flame may result in a decrease in thermocouple temperature, to a lower plateau. A rapid decrease in temperature is assumed to represent a burner being turned off or adjusted to a much lower setting. Differentiating these two events is done based on whether the temperature returns to baseline or to a new, lower plateau.
- Recognizing that heat generated at one burner causes temperatures to increase at adjacent burners (confirmed by controlled exploratory testing on several cooking ranges), the individual potential burner activity instances will be visually reviewed and coded as (a) confirmed distinct activity, (b) unlikely distinct (i.e., caused by transfer from another burner), or (c) indeterminate, i.e. possibly distinct individual burner activity.
  - If the timing of the temperature increase and decrease for one burner closely correlates or slightly lags with that of an adjacent burner, and the overall peak temperature is substantially lower for one or more burners with this temporal alignment, the event for the lower/lagging burner typically will be assumed to be caused by the burner with higher temperature and steeper change with time. All complex burner events will be reviewed by a second researcher and disagreements will be discussed and resolved.
  - For each confirmed burner activity we will record the number of minutes, providing a burner activity metric of burner-minutes.
- Distinct individual burner activities that overlap within 10 min will be combined into *cooking events*.
- Each cooking event will be characterized by recording or calculating the following:
  - Event start time, starting with activity of the first burner.
  - Event end time, when the temperature of the last burner in use starts to decrease with no subsequent plateau.
  - Event duration (min).

- Number of burners used, with two separate uses of the same burner, e.g. 10 min of burner activity, 4 min off, 8 min of burner activity, would count as two distinct burner activities but fall within a single cooking event.
- Number of burner minutes for each burner for the event.
- Locations of burners used: oven, front of cooktop, back of cooktop.
- Cooking events will also be identified and characterized using the temperature measured by the HOBO above, in the range hood.

#### Identify and characterize range hood use events

- Identify range hood use intervals and for each specify start and stop times, duration. Note speed/setting if discernible from data and calibration is available.
- Each range hood event will be characterized by recording or calculating the following:
  - Event start time
  - Event end time
  - Event duration (min).
  - Estimated speed setting for event if possible

Identification and analysis of pollutant events including those that occur coincident with cooking events ('cooking-linked pollution events')

#### Important notes about pollutant events:

- If the monitor was in the kitchen with the cooking burners, the NO2 and CO2 is expected to start increasing noticeably within a few minutes of the start of the cooking event. With the eLichens monitor in a separate room, the delay between the start of the cooking event and the start of pollutant events will differ between homes, owing to the different mixing or movement of air from the kitchen to the location of the monitor. The delay also could vary across events within a single home, owing to different room-to-room mixing conditions occurring throughout a day and with varying outdoor conditions, resulting in different directional air flows within the home.
- The timing of CO2 and NO2 increases from cooking burner use should be closely aligned, as the pollutants will be transported together. However, since CO2 has a higher background and is also emitted by occupants, the NO2 increase may appear earlier and more clearly.
- PM2.5 is produced in significant quantities in only some cooking events (especially frying), and may not be produced steadily throughout the events with emissions. For many cooking events that produce PM2.5, the emissions occur as a burst, sometimes within a very short interval.
- There are other sources of PM2.5 and CO2 and possibly, though less likely, NO2.

#### Identify and characterize pollutant events

- Identify events based on moderately to sharply increasing NO2, CO2, or PM2.5 up to a peak or plateau when the start of the increase closely follows the start of a cooking event. To be considered as a cooking-linked pollutant event, the pollutant concentration must start to increase within 10 min if only one room away and within 20 min if 2 or more rooms away, and end with similar or shorter delay relative to the end of the cooking event. (These times are imprecise and based on the experience of the research team reviewing data from homes, with relevant examples provided in Singer et al. 2017). The start time is the last point before the increase. The end time of emissions is the peak or the last point before concentration starts to drop, following a roughly steady, elevated level. Event / peak analysis starts with the identification and subtraction of the baseline or background contribution from long-duration sources including infiltration of outdoor pollutants (for PM2.5 and NO2) and occupant-generated CO2. We use the LOESS routine within the Python pyBaselines package to estimate the undisturbed values (baselines) for each pollutant and also for burner-adjacent and above the cooktop temperature series. This routine is referred to as RBE, robust baseline estimator, and is based on a locally estimated scatterplot algorithm with reweighting. The width of the rolling window is set to eight hours. The estimated baseline is subtracted from the time series of measured values to produce a time series of incremental concentrations resulting from events and activities. We use the Find Peaks routine within

- the Python SciPy package to identify events based on prominence over the baseline / background. The routine determines the peaks, and the associated start and end times.
- Calculate CO2, NO2 and PM2.5 event magnitudes (for all events whether cooking-linked or not) based on the prominence of the highest 10-minute average (compared to pre-event baseline) and integration of concentration above baseline, using manual and/or algorithmic detections of peaks. Integrated metric will have units of concentration \* time, (ppm-min for CO2, ppb-min for NO2, ug/m^3-min for PM2.5).
  - Peaks that occur within 10 min of each other (also an imprecise threshold based on experience of the research team), with intervening concentrations not dropping to <50% of the level of the first peak, shall be considered as being part of the same event.
  - Determine an event baseline based on the fitted baseline / background.
  - Events for which algorithmic classification provides nonsensical or undetermined results will be flagged and evaluated visually by at least two researchers.

For each pollutant event (PM2.5, NO2, CO2), we will calculate the following statistics:

- Event statistics:
  - start time and end time of *increasing* concentrations (i.e., not including the decay)
  - duration of emissions event
  - time of return to baseline (based on fitted baseline)
  - end of decay interval.
- Pollutant statistics:
  - prominence (highest ten-minute average above baseline) of each pollutant
  - integrated concentration of each pollutant above baseline (ug/m^3-min)

Notes:

- There should be few or no NO2 events that are not linked to cooking.
- There are unlikely to be any sharp CO2 events not linked to cooking; but there will be CO2 events linked to occupancy.
- There could be many PM2.5 events not linked to cooking.

All events identified by algorithms (Burners, cooking, range hood, PM2.5, NO2, CO2 increases) will be visually reviewed and any that are not deemed to be clearly correct will be reviewed and discussed with a second researcher.

Calculate Summary Statistics for each home during each of the pre- and post-intervention periods:

- Primary summary statistics of cooking and range hood events
  - Number of discrete events of individual burner use (confirmed and confirmed + possible) for cooktops, ovens, and any burner.
  - Number of cooking events.
  - Number and fraction of cooking events with substantial particle emissions.
  - Total burner minutes.
  - Mean (SD) number of burners used and burner minutes per cooking event (as an indicator of similarity).
  - Delay from start of cooking to start of range hood use.
  - Fraction of total burner minutes that reflects usage of the front burners and fraction that reflects usage of the back burners.
  - Fraction of cooking events with any range hood use.
  - Fraction of cooking events with range hood used for >80% of cooking burner use.
  - Fraction of cooking-linked pollution events that resulted in any range hood use and use for >80% of active burner time.
- Secondary summary statistics of self-reported cooking behaviors:
  - mean frequency of gas stove or oven use
  - mean frequency of the queried cooking methods (fried, deep fried, grilled, steamed/boiled, toasted, electric pot cooker, baked, microwaved)

- most common burner use (front or back)
  - mean frequency of range hood fan use
- Primary summary statistics of pollution events (PM2.5, NO2 and CO2). We will aggregate across all cooking-linked pollution events and all non-cooking-linked pollution events, both in the pre-intervention and post-intervention periods.
  - Means and SD of the:
    - prominences
    - pollutant concentrations above baseline
  - Number and fraction of pollutant events occurring without cooking burner use, including which have hood use
  - Total magnitude of emissions (total aggregated pollutant during cooking-linked pollution events divided by burner minutes)
- Secondary statistics
  - Time-integrated NO2 and NOx by Ogawa passive sampler
  - Time-integrated PM2.5 by eLichens (if discernible from the data)

## Outcome Definitions

At the baseline phone visit, health information was collected using the validated Isaac Questionnaires developed for use with 6-7 year-olds.(25) The core Isaac questionnaire contains 8 questions on asthma history, 6 on allergy history and 7 regarding history of eczema.

Children with asthma (with their parent) completed an asthma control test prior to or during each study visit. Study staff were trained on administering spirometry and FeNO tests for all participants, which occurred at follow up visits initially and later in the study was added to the initial visit to give children time to learn the techniques. These measures of respiratory status will be continuous variables.

The study used an EasyOne Spirometer, which was brought to the homes. Under the supervision of study staff, each child performed spirometry to complete three acceptable efforts (maximum eight attempts), in accordance with standard ATS/ERS performance criteria.(27) Each effort will be graded by a trained physician, in accordance with the 2019 ATS/ERS guidelines. If there are two or more efforts with acceptable quality and reproducible FEV1 and FVC (each  $\leq 0.15L$ ), the best FEV1 and best FVC will be used. If two or more efforts had usable quality and reproducible FEV1, but unacceptable FVC, only the best FEV1 will be used and FVC will be set to missing.

Each child also had a FeNO measured in accordance with ATS/ERS criteria,(28) by blowing a steady sustained exhalation into a NIOX Vero device to complete 2 measurements with exhalation duration greater than 10 seconds, and within 10% of each other (maximum eight attempts). If there are two measurements within 10%, this testing session will be graded as acceptable and the larger value will be used. If there are one or multiple FeNO measurements of adequate duration (but none within 10%), this testing session will be graded as usable and these values will be averaged to create the FeNO value for analysis.

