### Analysis Populations

All households for which we collected data for 3 or more cooking events both prior to and following the intervention will be included in exposure analyses. Children who successfully completed lung function testing both before and after intervention will be included in respiratory health outcomes. For households with data on more than one child, the child who has the most complete data (most spirometry and FeNO results that meet grading criteria for acceptable tests) will be used in the analyses.

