#### Determine if a cooking ventilation intervention is associated with changes in airways inflammation and lung function in children

##### asthma diagnosis allergies or eczema

[figure not shown]
We will also use Wilcoxon Signed Rank tests to compare the pre-intervention data to the post-intervention data to assess the relationship between intervention status and the following respiratory outcome variables. Given the small final sample size,

these will not be adjusted in the analysis (but original DAG maintained for completeness). Though we had initially intended to control for the number of visits with our team, only 2 of 14 participants had one

additional visit with our team prior to intervention, meaning that there is not enough variability in this variable to control for it.

[figure not shown]
1. Airways inflammation based on measured fractional exhaled nitric oxide (FeNO)
2. Airways obstruction based on measured forced expiratory volume in 1 second (FEV1) and the ratio of FEV1 to the Forced Vital Capacity (FEV1/FVC)
3. Self-reported lung health as measured by the asthma control test score (ACT)

Legend for the Three Directed Acyclic Graph Figures	
▶	exposure
●	outcome
●	ancestor of exposure
●	ancestor of outcome
●	ancestor of exposure and outcome
○	adjusted variable
○	unobserved (latent)
○	other variable
—	causal path
—	biasing path

**Assess whether cooking-related pollution is associated with respiratory outcomes in children.** We will use a simple visualization to do a rough exploration of these data. Due to the small sample size, we would be unable to control for all necessary confounders. But the original DAG is maintained for completeness. These will occur for the following sets of variables:

- Respiratory Health: ACT score, FeNO and FEV1
- Pollutants: PM2.5, NO2 and CO2, using measures a,b, and d listed above

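### FeNO is scored as the larger reading when two agree but as an average when none do, so a child whose session grade changes between visits has a maximum compared with a mean (about 2% per change of grade)

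*SAP*

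**What the plan says.** SAP, Outcome Definitions: a child makes up to eight attempts to obtain two FeNO readings of adequate duration within 10% of each other. If that succeeds, "this testing session will be graded as acceptable and the larger value will be used". If there are one or more readings of adequate duration but no agreeing pair, the session is graded usable and "these values will be averaged to create the FeNO value for analysis". The same section says that testing was at first done at follow-up visits and "later in the study was added to the initial visit to give children time to learn the techniques".

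SAP, Analysis Populations: "Children who successfully completed lung function testing both before and after intervention will be included in respiratory health outcomes". Nothing there requires the same grade on both occasions.

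SAP, Analysis Methods: "We will also use Wilcoxon Signed Rank tests to compare the pre-intervention data to the post-intervention data". FeNO is the first respiratory outcome listed, and the comparison is unadjusted. The Sensitivity Analyses section covers number of visits, hood replacements that were indicated but not done, and households with an asthmatic child. It has nothing on FeNO grade.

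**The concern.** The larger of two readings and the mean of the available readings estimate different quantities: the first sits above the child's true level on average, the second close to it. If a child is usable before and acceptable after, the recorded change includes that gap even when FeNO has not moved. The reverse sequence gives a spurious fall.

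The plan itself expects children to learn the technique. If learning raises the grade, changes of grade would run mostly from usable to acceptable, adding an upward component to an outcome hypothesised to fall. The risk is then partial masking of a benefit. With 14 participants and a rank test, even small systematic shifts can alter signs and ranks.

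**Working it through.** **Inputs from the documents.** Two-branch rule, 10% tolerance and maximum of eight attempts (SAP, Outcome Definitions); 14 participants and the Wilcoxon signed rank test (Analysis Methods); significance threshold 0.05 (Confidence Intervals and p-values; taken as two-sided); hypothesised FeNO fall of 7 ppb and minimum detectable change of 3.3 ppb at n = 30 (Power Considerations).

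**Assumed, because the documents give no figure.** Within-session coefficient of variation (CV) 3-12%; true FeNO 10-20 ppb; number of adequate readings per session; day-to-day variation.

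**1. The plan's yardstick.** The 3.3 ppb cannot be reproduced because no FeNO standard deviation is stated. At alpha 0.05 and power 0.80, a paired t-test with n = 30 detects 0.529 SD, which implies an SD of 3.3 / 0.529 = 6.2 ppb. With n = 14 the paired figure is 0.810 SD, or 0.810 × 6.2 = about 5 ppb. These serve only as a scale.

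**2. Algebraic limit.** How far the larger value can exceed the mean of an agreeing pair depends on what the 10% is taken of, which the SAP does not say:
- of the smaller reading: 1.10 / 1.05 = 1.048, so 4.8%;
- of the mean: 1.05 / 1.00, so 5.0%;
- of the larger reading: 1.00 / 0.95 = 1.053, so 5.3%.

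At 20 ppb the limit is therefore about 1 ppb.

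**3. Average excess.** Readings were simulated around an unchanged true level, stopping at the first agreeing pair.
- Acceptable sessions, larger value: about 1.6-2.2% above the true level with lognormal readings, and up to about 2.9% with normal readings, for CV 3-12%.
- Usable sessions, averaged: 0.1-0.4% above the true level with two or three lognormal readings at CV 3-10%.
- Mean of the agreeing pair: near zero.

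A child moving from usable (CV 10-30%) to acceptable (CV 5-8%) with no true change shows an average shift of +1.6% to +1.8%, and a recorded rise with probability 0.57-0.60.

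In ppb, using the wider range of 1.6-3%: 0.016 × 10 = 0.16 at the low end and 0.03 × 20 = 0.6 at the high end. Against 3.3 ppb that is 5% to 18%.

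**4. When the averaging branch is used.** With eight adequate readings at CV 3-12%, practically every session yields an agreeing pair. At CV 8%, about 40% of sessions are usable with two adequate readings and about 5% with three. Grade changes therefore need sessions with only one to three adequate readings.

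**5. Effect on the test.** Simulation with 14 children, no true change and day-to-day variation of 0-5%; nominal rate 2.5% in each direction:

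| Children moving usable to acceptable | Rate of a significant rise |
|---|---|
| 4 | 3.3-3.5% |
| 7 | 4.6-5.0% |
| 14 | 7.6% |

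With 20% day-to-day variation, the rate for all 14 falls to 4.3%.

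**6. After the fix.** With means in both grades, the shift for a child changing from usable to acceptable becomes -0.3% to -0.5% (-0.05 to -0.10 ppb at 20 ppb). With all 14 moving, the rate of a significant rise is 2.2-2.8%.

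**The case against.** The case that this is immaterial has real force.

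- **Scope.** A reader might infer that any child whose technique improves will show an artificial rise. The rule does not do that. The shift arises only when the grade changes; improvement within the acceptable grade adds almost nothing (CV falling from 20% to 5% with eight attempts moves the excess only from about 1.6% to 2.0%). Even a child who does move up has only a 0.57-0.60 chance of a recorded rise.
- **Direction.** A reader might also infer that the study's FeNO result is biased upward. The documents give no grade counts by visit, so the net direction is unknown and the net effect could be nil. Protocol section 9a has FeNO tested at visits 1 and 2, both before the intervention has had time to act, so later households had practice before the visit 2 measurement. This does not help households enrolled earlier, and the SAP does not say which pre-intervention session supplies the pre value.
- **Consequence.** This is a pilot that states it is underpowered. A net upward shift would oppose the hypothesis and so would not manufacture a benefit.
- **Late change.** The SAP's revision history places version 4 while analyses were being completed, so a new outcome derivation now is a post hoc change.

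All four points stand as limits on size and certainty. None removes the inconsistency: the two summaries differ, the paired test mixes them, and no planned analysis would show whether it mattered.

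**Conclusion.** This is a real but minor inconsistency. A change from usable to acceptable adds about 2% on average to the recorded FeNO change (roughly 1.6-3%; 0.2-0.6 ppb at 10-20 ppb), and the opposite change subtracts it. If practice improves grades, the net shift is upward, against the hypothesised fall. It is well below the stated 3.3 ppb, and further below the roughly 5 ppb implied for 14 children.

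The size rests on the assumed CVs, error distribution and FeNO level, and on treating usable averages as close to unbiased. Single sessions can differ by more: readings of 12, 20 and 22 score 22, while 12, 20 and 22.5 score (12 + 20 + 22.5) / 3 = 18.2. How many children changed grade, and hence whether the result was affected, cannot be determined from the documents.

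**What to change.** Score FeNO as a mean in both grades: the mean of the two agreeing readings for acceptable sessions, and the mean of the adequate-duration readings for usable sessions. Recalculate from the individual readings, assuming these were kept. Enter this as a dated SAP revision that says how far the analyses had progressed, and report the result under the current rule alongside as a sensitivity analysis. Tabulate session grade by visit so that readers can see how many children changed grade and in which direction. State which pre-intervention session supplies the pre value.

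The cost is a few lines of text and a recalculation, with no new data. The downside is a small, disclosed, late change to an outcome derivation in an uncontrolled before-after study, which is why both versions should be shown. A mean in both grades removes the gap between maximum and mean. It does not remove the separate jump when an outlying reading is dropped because two others agree: in the example above, the scores become 21 and 18.2.
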